**Figure 2. Sequential Monitoring Rules for Efficacy and Futility in NSCLC Arm**

**Table 11. Decision Rules based on Efficacy Bounds for NSCLC Arm**

Monitoring Point (# subjects)	Minimum # Responders to Determine Efficacy
10-12	4
13-18	5
19-24	6
25-30	7
31-36	8
37-42	9
43-44	10

**Table 12. Decision Rules based on Futility Bounds for NSCLC Arm**

Monitoring Point (# subjects)	Maximum # subjects w/ response to declare Futility
10-14	0
15-20	1
21-26	2
27-32	3
33-38	4
39-44	5

**Table 13. Operating Characteristics of Sequential Monitoring Approach for NSCLC Arm**

True RR	Probability of Declaring Futility	Probability of Go at end of Study	Average Sample Size
10%	0.87	0.05	24.9
15%	0.58	0.25	32.2
20%	0.29	0.55	38.1
25%	0.12	0.80	41.5
30%	0.04	0.93	43.1
35%	0.01	0.98	43.7

**11.2 Analytic Plan for Primary Objectives:**

We will use mRECIST criteria to determine brain metastasis response rate (BMRR). The proportion of patients with a brain metastasis response in the clinically evaluable lesion(s) will be calculated along with a 95% confidence interval.

**11.3 Analytic Plan for Secondary Objectives:**

- (1) Best overall response rate (ORR) is defined as the percentage of patients who experience a CR or PR in any metastases (clinically evaluable cerebral or systemic) as determined by mRECIST criteria in the brain or RECIST criteria in the body. The proportion of patients

with an ORR will be calculated with a 95% confidence interval. A similar analysis will be performed using ir-mRECIST and ir-RECIST.

- (2) B7-H1 (PD-L1) expression and other potential biomarkers will be correlated to clinical endpoints. Exploratory, hypothesis-generating analyses will be performed.
- (3) Progression-free survival will be calculated as the time from start of MK-3475 to progression (using mRECIST criteria for brain lesions and RECIST criteria for systemic disease) or death. Overall survival will be calculated as the time from start of MK-3475 to death. Patients who do not meet the endpoint will be censored at the date of last follow-up. PFS and OS will be determined separate for each arm and median survival will be estimated by using Kaplan-Meier methodology
- (4) Safety and toxicity will be assessed using CTC v4.0 criteria. All participants who receive any amount of study drug will be evaluable for toxicity.

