### **10.3 Evaluation of Best Overall Response**

The Best Overall Response is the best response recorded from the start of the treatment until disease progression/recurrence (taking as reference for progressive disease the smallest measurements recorded since the treatment started). The patient's best response assignment will depend on the achievement of both measurement and confirmation criteria. The best response will take into consideration both the clinically evaluable brain metastases and systemic metastases, and therefore will include measurements from both mRECIST criteria (in the brain) and RECIST criteria (in the body) as follows:

Complete Response (CR): Disappearance of all target lesions in the brain and systemic disease.

Partial Response (PR): Partial response in both the brain and the systemic disease, or if there is PR at one site and SD at the other, the sum of diameters from the brain and systemic disease will be added and the best overall response will be considered PR if there is at least a 30% decrease, taking as reference the baseline sum diameters.

Progressive Disease (PD): Progressive disease in either the brain or the systemic disease will qualify as PD as the best overall response.

Stable Disease (SD): Stable disease in both the brain and systemic disease, or if the sum of diameters from the brain and systemic disease does not qualify for PR or PD (at least a 20% increase in the sum of diameters of target lesions), taking as reference the smallest sum diameters since the treatment started.

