## 11.4 Reporting and Exclusions

11.4.1 **Evaluation of toxicity.** All patients will be evaluable for toxicity from the time of their first treatment with MK-3475.

11.4.2 **Evaluation of response.** All patients included in the study must be assessed for response to treatment, even if there are major protocol treatment deviations or if they are ineligible. Each patient will be assigned one of the following categories: 1) complete response, 2) partial response, 3) stable disease, 4) progressive disease, 5) early death from malignant disease, 6) early death from toxicity, 7) early death because of other cause, or 9) unknown (not assessable, insufficient data). [Note: By arbitrary convention, category 9 usually designates the “unknown” status of any type of data in a clinical database.]

All of the patients who met the eligibility criteria (with the possible exception of those who received no study medication) should be included in the main analysis of the response rate. Treatment response includes categories 1 and 2 (complete and partial response). Patients in response categories 4-9 should be considered to have a treatment failure (disease progression). Thus, an incorrect treatment schedule or drug administration does not result in exclusion from the analysis of the response rate. Precise definitions for categories 4-9 will be protocol specific.

Conclusions will be based on all eligible patients. Sub analyses may then be performed on the basis of a subset of patients, excluding those for whom major protocol deviations have been identified (e.g., early death due to other reasons, early discontinuation of treatment, major protocol violations, etc.). However, these sub analyses may not serve as the basis for drawing conclusions concerning treatment efficacy, and the reasons for excluding patients from the analysis should be clearly reported. The 95% confidence intervals will also be provided.

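### Sections 11.3(1) and 10.3 define best overall response rate by incompatible rules: a response at either site versus one combined brain-and-body category

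*Combined protocol and SAP*

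**What the plan says.** Section 1 lists overall response rate among the four measures by which efficacy will be judged, and Section 1.2 makes it the first secondary endpoint.

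**Section 11.3(1)** states that best overall response rate "is defined as the percentage of patients who experience a CR or PR in any metastases (clinically evaluable cerebral or systemic". Each site is judged on its own criteria, joined by an or: the response counts "as determined by mRECIST criteria in the brain or RECIST criteria in the body". The section has no pooled sum and no override for progression at the other site. The rate is to be reported with a 95% confidence interval, and a similar analysis is promised under ir-mRECIST and ir-RECIST.

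**Section 10.3**, which is devoted to best overall response, builds one category per patient from both sites:

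- CR needs target lesions to disappear in both the brain and the body.
- PR is "Partial response in both the brain and the systemic disease, or if there is PR at one site and SD at the other". In the second case the two sums are added, and "the best overall response will be considered PR if there is at least a 30% decrease" from baseline.
- SD covers stable disease at both sites, and also applies "if the sum of diameters from the brain and systemic disease does not qualify for PR or PD".
- "Progressive disease in either the brain or the systemic disease will qualify as PD as the best overall response".
- The time window is set by "The Best Overall Response is the best response recorded from the start of the treatment until disease progression/recurrence".

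**Section 11.4.2** adds that "Each patient will be assigned one of the following categories". It counts complete and partial response as treatment response and counts progression as failure. It does not mention ORR by name and cites neither 10.3 nor 11.3(1).

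**The concern.** The two sections use one name for two different quantities. The 11.3(1) rule asks whether either site responded; the 10.3 rule asks whether the patient responded overall. They part in two situations:

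1. **Response at one site, SD at the other.** This is always a response under 11.3(1). Under 10.3 it is SD overall when the pooled fall is under 30%.
2. **Response at one site, PD at the other at or before that response.** This is a response under 11.3(1) and PD under 10.3. It can arise because Section 4.8 allows treatment to continue beyond PD, so a response elsewhere can still be recorded and confirmed. If the progression is confirmed, Section 10.5 would date the patient's PFS event to the first progression scan, while 11.3(1) still counted the patient as an overall responder.

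Progression after a confirmed overall response causes no conflict, because 10.3 takes the best response up to progression.

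At stake is the reproducibility of a named efficacy measure. If the choice is left open until the scans have been read, the more favourable figure could be selected. Brain metastasis response rate (BMRR) and its monitoring boundaries use neither rule and are not affected.

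**Working it through.** The plan states no expected value, threshold or sample size for ORR, so there is no figure to reproduce. The check classifies example patients under both rules.

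**Inputs.** Evaluable brain lesions are at least 5 mm and under 20 mm, and one is enough (Sections 3.1 and 4.2). Up to five brain lesions are summed (Section 10.1). Body targets are at least 10 mm on CT (Section 10.2). PR is a fall of at least 30% from baseline. Planned numbers are 20, 44 and 10 (Section 11.5). The lesion sizes below are illustrations.

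**Formula.** With brain sums b0 to b1 and body sums s0 to s1, in mm:

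pooled change = [(b1 + s1) − (b0 + s0)] / (b0 + s0)

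| Case | Brain | Body | Pooled change | 11.3(1) | 10.3 |
|---|---|---|---|---|---|
| a | 10 to 5 (PR) | 10 to 10 (SD) | −5/20 = −25.0% | response | SD |
| b | 15 to 15 (SD) | 20 to 12 (PR) | −8/35 = −22.9% | response | SD |
| c | 10 to 0 (CR) | 30 to 30 (SD) | −10/40 = −25.0% | response | SD |
| d | PR | new lesion, same scan (PD) | not relevant | response | PD |
| e | 45 to 22.5 (PR) | 20 to 20 (SD) | −22.5/65 = −34.6% | response | PR |
| f | 10 to 10 (SD) | 60 to 36 (PR) | −24/70 = −34.3% | response | PR |

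The rules disagree in a to d and agree in e and f.

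**When a brain response is lost in the pool.** Suppose the brain sum b falls by a fraction r and the body sum S is unchanged. The pooled fall is br/(b + S). It reaches 30% only if

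S ≤ b(r − 0.30)/0.30

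- b = 10, r = 0.5: S ≤ 10 × 0.20/0.30 = 6.7 mm, below the 10 mm minimum for a body target.
- b = 19, r = 0.5: S ≤ 19 × 0.20/0.30 = 12.7 mm.
- b = 10, r = 1 (brain CR): S ≤ 10 × 0.70/0.30 = 23.3 mm.
- Any single brain lesion under 20 mm with r up to 0.45: S must be below 20 × 0.15/0.30 = 10 mm. Such a patient cannot be PR under 10.3 if any measurable body target is unchanged.

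**Direction.** The pooled change is a weighted average of the two site changes, so two falls that are each under 30% cannot pool to 30%. A 10.3 response therefore always includes a CR or PR at one site at least. With the same patients and confirmation rules, every 10.3 responder is an 11.3(1) responder, and the 11.3(1) rate is never the lower one.

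**Effect per reclassified patient.** 1/20 = 5.0 points (melanoma), 1/44 = 2.3 points (NSCLC Cohort 1), 1/10 = 10.0 points (Cohort 2). With assumed responder counts and exact 95% intervals, one reclassified patient gives:

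- n = 20: 7/20 = 35.0% (15.4 to 59.2) versus 6/20 = 30.0% (11.9 to 54.3).
- n = 44: 11/44 = 25.0% (13.2 to 40.3) versus 10/44 = 22.7% (11.5 to 37.8).

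**The case against.** **Section 11.4.2 already settles it.** It wants one category per patient and treats progression as failure. Only 10.3 builds such a category, and an either-site rule cannot give a single category to a patient with PR in one place and PD in the other. This has weight and shows which way the plan leans. But it is general text that does not mention ORR, and it cannot displace an explicit definition in 11.3(1).

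**Section 11.3(1) may be shorthand.** The phrase about cerebral or systemic lesions could merely describe scope, in contrast to the brain-only BMRR, leaving 10.3 to supply the definition. That may be what was intended. The wording, CR or PR in any metastases, does not say so.

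**Cases c and d are interpretations.** Section 10.3 has no line for CR with SD, and it does not say whether unconfirmed progression fixes the category. On c, the residual SD clause covers a pooled fall under 30%. On d, the PD clause in 10.3 has no confirmation condition; that condition is in the PFS definition (Section 10.5). If confirmation were read in, d would still conflict whenever the progression was confirmed. What does stand is that 10.3 leaves open how to treat body progression that falls between a first brain response and its confirmation. Cases a and b need none of this.

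**Little depends on it.** ORR carries no hypothesis, alpha or boundary, and the examples use small sums. This is correct, and it limits the importance of the point without removing the contradiction.

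**Conclusion.** The contradiction is real. Both passages are current, both use the term best overall response, and they classify the same patient differently in two identifiable situations. The direction is fixed: on the same patients and confirmation rules, 11.3(1) gives a rate equal to or higher than 10.3.

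The total size cannot be stated. The plan gives no information on how often brain and body responses agree, so the number of reclassified patients is unknown and may be zero. The lesion sizes and responder counts used above are assumptions for illustration. The consequence is confined to a descriptive secondary endpoint and its immune-related counterpart. The plan should be corrected, but the primary conclusion of the trial does not depend on it.

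**What to change.** Reconcile the two sections so that ORR has one definition. The simplest wording for 11.3(1) is: *ORR is the percentage of patients whose best overall response, as defined in Section 10.3, is CR or PR.* This fits the single-category scheme in 11.4.2. If the either-site rate is wanted, keep it under a separate name, such as any-site response rate. If the sponsor in fact meant the either-site rule for ORR, 10.3 should say that its combined category does not determine ORR.

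State that the same combination rule applies to the analysis under ir-mRECIST and ir-RECIST, because 10.3 mentions only mRECIST and RECIST.

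While 10.3 is open, it would help to add the category for CR at one site with PR at the other, for CR with SD when the pooled fall is at least 30%, and for patients without measurable extracranial disease. These are gaps in detail and separate from the contradiction.

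The cost is one sentence in 11.3(1), a clause for the immune-related analysis and up to three optional lines in 10.3. No new data, scans or visits are needed. The drawback is that the reported ORR may be lower than under the either-site rule.

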#### 4.7 Duration of Therapy

In the absence of treatment delays due to adverse event(s), treatment may continue for up to 2 years or until one of the following criteria applies:

1	Disease progression (see Section 4.8)
2	Symptomatic deterioration of health status without objective evidence of disease progression. Every effort should be made to document objective progression of disease in such cases.
3	Imminent risk in the case of progressing lesion or new/worsening edema seen on brain MRI
4	Unmanageable toxicity most probably attributed to MK-3475 (see Table 2)
5	Development of intercurrent illness limiting the ability to comply with study or the development of uncontrolled concurrent illness that prevents further administration of treatment or confound the ability to interpret data
6	General or specific changes in the patient's condition rendering the patient unacceptable for further treatment in the judgment of the investigator
7	Patient request for discontinuation, patient withdrawal from study, or patient lost to follow up
8	Development of neurologic or systemic complications following local therapy to any lesion
9	Death
10	Study termination by sponsor

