**6.3 Follow-up Visits**

All patients who discontinue the study treatment will have a follow up visit at Day 28 ±7 days from the last study treatment.

- 1) History and physical examination
- 2) Measurement of height, weight and vital signs (including blood pressure, heart rate, respiratory rate, oxygen saturation, and temperature).
- 3) Performance status evaluation
- 4) Review concomitant medications
- 5) Adverse events assessment
- 6) CBC with differential, serum chemistry (Na, K, Cl, CO2, BUN, creatinine, glucose, calcium), magnesium, phosphate, liver function tests (albumin, total protein, alkaline phosphatase, total and direct bilirubin, ALT, AST), LDH
- 7) Tumor assessment with CT scan of the chest/abdomen/pelvis and brain MRI with perfusion, if possible, should continue every 8 weeks (+/- 5 days) until progression, withdrawal of consent, death, lost to follow-up, or start of a subsequent anti-cancer therapy

All patients who discontinue early or who complete the study treatment period will be followed for survival. Survival follow-up information will be collected via telephone calls, patient medical records, and/ or clinic visits every 3 months +/- 14 days until death, loss to follow-up or study termination. All patients will be followed for survival unless the patient requests to be withdrawn from follow-up. If the patient withdraws from study treatment but not from follow-up, the study staff may use a public information source to obtain information about survival status.

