### **10.5 Progression-Free Survival (PFS)**

PFS is defined as the time from initiation of study drug until the first documented, confirmed progression of clinically evaluable brain metastases based on mRECIST criteria, systemic disease based on RECIST criteria, or death. If there is progression of disease that is then confirmed on a follow up scan at least 4 weeks later, the initial date of documented progression should be used in the PFS analysis.

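### PFS shares the OS censoring rule, so a patient who starts new therapy without progression can be censored at a survival contact with no scan behind it

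*Combined protocol and SAP*

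**What the plan says.** Section 11.3(3) sets the PFS clock and event: "Progression-free survival will be calculated as the time from start of MK-3475 to progression", by mRECIST in the brain and RECIST in the body, or death. OS follows, and then one censoring sentence for both: "Patients who do not meet the endpoint will be censored at the date of last follow-up". Medians are estimated by Kaplan-Meier, separately for each arm.

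Section 10.5 also defines PFS ("PFS is defined as the time from initiation of study drug until the first documented, confirmed progression", or death) but gives no censoring rule.

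Section 6.3 sets two follow-up schedules after treatment stops. The rule for tumour imaging (MRI of the head, CT of the body) reads: "should continue every 8 weeks (+/- 5 days) until progression, withdrawal of consent, death, lost to follow-up, or start of a subsequent anti-cancer therapy"; footnote E of the study calendar repeats this. Survival information is collected by telephone, medical records or "clinic visits every 3 months +/- 14 days until death, loss to follow-up or study termination". If a patient withdraws from treatment but not from follow-up, "the study staff may use a public information source to obtain information about survival status". Section 4.9, on the duration of follow-up, describes survival follow-up until death.

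Section 4.7 lets treatment stop without documented progression, for example for "Symptomatic deterioration of health status without objective evidence of disease progression", toxicity, intercurrent illness or patient request.

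**The concern.** A censoring date for PFS should be a date on which the patient was known to be free of progression. That takes a tumour assessment. A telephone call or a public record shows only that the patient was alive.

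Once a patient without progression starts another therapy, Section 6.3 stops the scans, so later progression cannot be recorded. The survival contacts continue, and the latest becomes the date of last follow-up. The patient then stays in the PFS risk set, event-free, over a period in which nobody looked. If the patient dies on the next therapy, the PFS event is dated at that death, however long after the last scan.

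Median PFS is a named efficacy measure (Sections 1 and 1.2(3)). The trial has no control arm in which the same distortion could cancel, and benefit from the next therapy could be read as PFS on MK-3475.

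**Working it through.** **Who is affected**

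| Situation | Scans after stopping MK-3475 | Survival contact | PFS date under 11.3(3), read literally |
|---|---|---|---|
| Progression documented | End at progression | Continues | Progression date: no problem |
| Stops drug, no new therapy | Continue 8-weekly | Continues | Scans support the date: essentially no problem |
| Starts new therapy, no progression | End | Continues 3-monthly | Last survival contact, or death |

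Only the last row is at issue. It reaches the estimate by two routes. A switcher still alive is censored too late through the censoring sentence. A switcher who dies becomes a late event through the endpoint definition, progression or death.

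**Size**

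The plan gives no target median, event count or power for PFS, so there is no stated figure to reproduce. What follows is illustration.

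From the documents: scans every 8 weeks, W = 56/30.4375 = 1.84 months; survival contacts every 3 months; 36-month NSCLC accrual (11.5). A progression median of 4 months and an OS median of 12 months are borrowed from the background on chemotherapy (2.5 and 2.1.2). They are not design inputs. Assumed: exponential times, other medians, 12 months minimum follow-up, and the switching fraction f.

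*Model A: switching unrelated to prognosis (200,000 patients per scenario).* P, D, X and C are the times of progression, death, switch and end of follow-up. The hazards are λp = ln 2/(progression median), λd = ln 2/(OS median) and λs = f/(1 − f) × (λp + λd). For medians of 4 and 12 months and f = 0.1, λs = 0.1/0.9 × (0.1733 + 0.0578) = 0.0257 per month. Progression is seen at W × ceil(P/W).
- Written rule: a switcher is an event at D if D < C, otherwise censored at 3 × floor(C/3).
- Last-scan rule: a switcher is censored at W × floor(min(X, D, C)/W).

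| Progression / OS median (months) | 12-month PFS, everyone scanned | Written rule, f = 10 / 20 / 30% | Last-scan rule | Median under written rule (everyone scanned) |
|---|---|---|---|---|
| 4 / 12 | 7% | 12 / 17 / 23% | 7% | 3.7 / 3.7 / 4.2 (3.7) |
| 4 / 24 | 10% | 17 / 23 / 30% | 10% | 3.7 / 5.5 / 5.5 (3.7) |
| 8 / 24 | 27% | 30 / 33 / 37% | 27% | 7.4 / 7.4 / 7.4 (7.4) |

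The excess in 12-month PFS is 3 to 7 points at f = 10% and 10 to 20 points at f = 30%. The median is less sensitive because documented progressions fall on the scan grid. The largest shift, 5.52 − 3.68 = 1.84 months, is one scan interval.

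*Model B: switch uniformly distributed before progression (400,000 patients).* Progression median 3 months, follow-up 12 to 36 months.

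| Median survival after progression | 6-month PFS, everyone scanned | Written rule, f = 10 / 20 / 30% | Last-scan rule | Median, written rule | Median, last-scan rule |
|---|---|---|---|---|---|
| 7 months | 28% | 33 / 38 / 43% | 29 / 31 / 33% | 3.7 / 5.1 / 5.5 | 3.7 |
| 1 month | about 28% | 28 to 30% | 29 to 33% | 3.7 | 3.7 |

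With 7 months and f = 30%, the written rule is 43 − 28 = 15 points too high. Last-scan censoring is still 33 − 28 = 5 points too high, because leaving just before progression is informative. With 1 month, death follows so soon that the written rule is the less biased of the two. In the 7-month case most switchers die during follow-up, so the treatment of deaths carries much of the shift. Moving the censoring date alone would not remove it.

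**The case against.** Several points against the concern have force.

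- **The phrase is ambiguous.** The study calendar separates a follow-up visit, which carries CT and MRI, from long-term follow-up, which carries survival only. An analyst could take last follow-up for PFS to mean the last scan. But Section 4.9 uses the term for survival follow-up, and no section ties PFS censoring to a scan. The choice should not wait until results are visible.
- **The group may be small.** A reader might infer that every patient who stops under Section 4.7 is affected. The text does not support that. Scans continue after discontinuation unless new therapy starts or another listed end point occurs. Section 4.7 asks for every effort to document progression when a patient deteriorates, and Section 10 allows early imaging.
- **Deaths after a switch are an estimand question.** Counting them follows from the definition in 10.5 and 11.3 and is a legitimate choice. It is not an error in the censoring sentence.
- **Last-scan censoring is not neutral.** A reader might infer that it removes the bias, or that the bias is always largest in patients who switch because they are deteriorating. Model B contradicts both.
- **The plan reports the median.** The 6- and 12-month rates are not planned outputs, and the median does not move at 10% switching in any scenario run.

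These points limit the size and rank of the problem. They do not supply the missing PFS censoring rule.

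**Conclusion.** The point stands as a moderate correction to a secondary endpoint. As written, the shared rule censors PFS at a contact without tumour assessment for patients who start new therapy without progression, and this tends to inflate PFS. In the scenarios run, the median shift ranges from none (all scenarios at 10% switching, and some at 30%) to about 1.8 months at 30%. Those figures combine the censoring route and the death route. They rest on assumed switching fractions, progression and survival medians and follow-up, none of which the plan gives for this population.

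A reader might infer that the trial's conclusion is at risk, or that the change is essential before the trial can be interpreted. The documents do not support that. PFS is descriptive, with no hypothesis, alpha or decision rule, and the go/no-go decision in Section 11.1 rests on brain metastasis response, which this rule does not touch.

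**What to change.** 1. Split the sentence in 11.3(3). Censor OS at the date last known alive. Censor PFS, for patients without documented progression or death, at the last adequate tumour assessment (brain MRI plus body imaging) on or before the start of any subsequent anti-cancer therapy.
2. State in both 10.5 and 11.3 whether deaths after a switch count as PFS events, and report the alternative as a sensitivity analysis.
3. Because last-scan censoring is informative when patients leave before progression, add a sensitivity analysis that counts the start of new therapy, or stopping for symptomatic deterioration, as a PFS event.
4. Record the date of first subsequent anti-cancer therapy at the Day 28 visit and the 3-monthly contacts. Section 6.3 already needs that date to end imaging.

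The cost is wording in two sections, one date field at contacts already scheduled, and a little more analysis. No visit, scan or patient is added. The reported PFS will usually be slightly less favourable, though Model B shows that this is not guaranteed.
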